Each participant should be scanned using the same machine throughout the study. In case of machine change, or hardware/software upgrade the necessity to complete another test scan using the new equipment should be agreed upon with the central imaging core lab.

8.1.2	Disability Assessments					
8.1.2.1	Expanded	Disability	Status	Scale/	CCI	
CCI						

The EDSS is a neurological assessment to evaluate disability in neurologic deficient patients with MS. It will be completed by the evaluating physician, who evaluates the participant's state according to the KFS Grades. The repeated application allows the measurement of the level of disability over time (Kurtzke 1983).

An EDSS progression is defined as an increase in the EDSS scale as follows:

- If the Baseline* EDSS score is 0, the increase must be > 1.5 units
- If the Baseline* EDSS score is ≥ 0.5 or ≤ 4.5 , the increase must be ≥ 1.0 units
- If the Baseline* EDSS score > 5.0 the increase must be > 0.5 units

Sustained EDSS progression is defined as EDSS progression (as defined above) confirmed by subsequent measurements of at least 3 months apart.

*The extension study-specific starting point for analyses is the parent study baseline (before the initial dose of cladribine tablets).

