8.1.5 No Evidence of Disease Activity

No evidence of disease activity (NEDA), also referred to as freedom from disease activity, is a new goal that is emerging in MS treatment. The NEDA-3 is a composite measure including 3 parameters: relapses, cognition and disability progression, and MRI activity, and is derived in the analysis phase. NEDA-3 is defined as the absence of the following 3 conditions:

- Qualifying Relapses (as defined in Section 8.1.3)
- CDP (as defined in Section 8.1.4)
- MRI activity (new/enlarging T2 lesions and/or T1 Gd+ lesions; see Section 8.1)

during the defined period.

Patient Diary 8.1.8

At the Baseline Visit, participants will be provided with a diary to record details on AEs, and concomitant medications and procedures (Appendix 6). The participant will receive instructions regarding the filling out of the diary.

The patient diary entries must be reviewed by the study coordinator(s)/nurse(s) with the participant to clarify any discrepancies and ensure proper completion. This review must be completed at each visit and the review recorded in the participant's clinic visit notes. The appointed designee will enter in the eCRF (on the correct form, i.e., the AE or concomitant medications and procedures form) what each participant records on his/her form and any information that is obtained after subsequent questioning of the participants.

8.1.9 **Data Retrieved from Parent Study**

Data from the parent study will be retrieved in the analysis phase, including previous measurements of efficacy assessments, demographic characteristics, and medical history obtained as part of the parent study.

8.2 **Safety Assessments and Procedures**

The safety profile of cladribine tablets (concerning long-term effects) will be assessed through the recording, reporting and analysis of baseline medical conditions, AEs, physical examination findings, vital signs, and laboratory tests. At each study visit (Section 1.3), the participant will be gueried on changes in his or her disease condition. Comprehensive assessment of any potential toxicity experienced by each participant will be conducted starting when the participants give informed consent and throughout the study. The Investigator will report any AEs, whether observed by the Investigator or reported by the participant; the reporting period is specified in Section 8.3.1. All AEs and SAEs must be reported on the appropriate eCRF page as described in Appendix 7.

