- 6-months confirmed disability progression (6MCDP), is used in the IAP to keep consistent with the parent study IAP, although 3 months confirmed disability progression, 3MCDP, is defined in the CSP.
- As data provided from MRI vendor only contains absolute values for (all) T1-Gd+ lesions per assessment (no new T1-Gd+ lesions), in consequence (all) T1-Gd+ lesions per assessment will be used for definition of disease activity and for calculation of Combined Unique Active (CUA) lesions during MAGNIFY MS Extension Study. However, as MAGNIFY MS Extension Study only has yearly MRI assessments the number of "new" and "all" T1-Gd+ lesions can be considered identical (see also explanation in Section 9.8).

8 Analysis Sets and Subgroups

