14.1.1 Primary Objective: Derivation and analysis of the primary endpoint

No Evidence of Disease activity (NEDA), also referred to as freedom from disease activity, is a new goal that is emerging in MS treatment. NEDA is a composite measure of disease activity, including relapses, cognition and disability progression, and MRI activity.

NEDA-3 during the Extension Study Period is defined as absence of the following three events during the Period:

- Qualifying Relapses
- 6-months Confirmed Disability Progression (6MCDP, see definition below)
- MRI Activity (i.e., presence of T1 Gd+ lesions and/or active T2 lesions)

NEDA-3 will be analyzed with the Kaplan-Meier (KM) time-to-event method to reduce the impact of unknown/missing information.

The start date will be the end date of M24 Visit + 1.

The event date will be defined as the minimum of

- the onset date of the first qualifying relapses during the Extension Study Period
- the start date of the first 6MCDP during the Extension Study Period (see definition below)
- the scan date of the first MRI during the Extension Study Period where at least one T1 Gd+ lesion or at least one active T2 lesion (see Section 9.8 for definition) is identified.

Imputation of partial onset dates of relapses is described in Section 9.7. Since full dates of MRI scan and EDSS assessment are mandatory, partial dates of 6MCDP, or MRI Activity are not expected.

If the participant did not experience any of the three events described above during the Extension Study Period, the minimum of the scan date of the last available MRI, the assessment date of the last available EDSS, and the Extension Study completion/discontinuation date will be used as the censoring date.

The time to disease activity (in months) will be calculated as [event date or censoring date as applicable – start date + 1]/30.4375. The number of participants at risk, failed, and survival rate (i.e., the proportion of participants with NEDA-3) along with the 95% CI will be estimated as per the KM method and reported at 6-months intervals. The KM survival curve will be plotted as well.

A descriptive summary of number and proportion of participants with event (overall and by type of event, i.e., qualifying relapse, 6MCDP, or MRI activity as the earliest event) and censored will be also presented.

6MCDP

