The 6MCDP during Extension Study Period is defined as sustained increase in EDSS score that started during the Period. A Sustained Increase in EDSS score is defined by an increase of:

- at least 1.5 points if the Baseline EDSS score was 0, or
- at least 1 point if Baseline EDSS score was between 0.5 and 4.5 inclusively, or
- at least 0.5 point if the Baseline EDSS score was at least 5,

that occurs over a 6-months' time-period.

The increase will be defined as sustained when it occurs on two post-Baseline Visits during the Extension Study Period that are at least 166 days apart (to be consistent with the parent study minimum visit gap) and no observations at any other visits (including unscheduled visits) in between are less than the defined increase. The assessment date of the earlier of the two EDSS assessments with the defined increase will be defined as the start date of 6MCDP.

For descriptive summaries the following rules will be defined:

Qualifying Relapse

- Yes: any qualifying relapse reported during the Extension Study Period,
- No: Extension study period completed, and no qualifying relapse reported during the Extension Study Period,
- Unknown: otherwise.

6MCDP

• Yes: sustained increase in EDSS score that started during the Extension Study Period,

- No: at least 2 post-Baseline EDSS assessments that are 166 (or more) apart and no sustained EDSS progression that started during the Extension Study Period,
- Unknown: Otherwise.

MRI activity

- Yes: any T1-Gd+ or active T2 observed during the Extension Study Period,
- No: at least one post-Baseline MRI and no T1-Gd+ or active T2 observed during the Extension Study Period,
- Unknown: otherwise.

Analysis (Analysis Set)	Derivation	Statistical Analysis Methods	Missing data handling		
	Primary endpoint: Proportion of participants with NEDA-3 during Year 3 Visit and Year 4 Visit Period after the initial dose of cladribine tablets				

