14.1.2 Primary Objective: Sensitivity Analyses of the Primary Endpoints

The robustness of the results of the primary analysis will be evaluated by the following:

- The primary analysis will be repeated on the TCS
- The primary analysis will be repeated by subgroup "Previous treatment with DMDs" on the FAS.

Analysis (Analysis Set)	Derivation	Statistical Analysis Methods	Missing data handling
	oint: Proportion of participants se of cladribine tablets	with NEDA-3 during Year 3 Visit a	and Year 4 Visit Period after
Sensitivity (TCS)	Same as in the Primary Analysis (see Section 14.1.1)	Same as in the Primary Analysis (see Section 14.1.1)	Same as in the Primary Analysis (see Section 14.1.1)
Sensitivity (FAS by subgroup "Previous treatment with DMDs")	Same as in the Primary Analysis (see Section 14.1.1)	Same as in the Primary Analysis (see Section 14.1.1) with KM estimates reported by subgroup.	Same as in the Primary Analysis (see Section 14.1.1)
Sensitivity (FAS)	Crude percentages and time to event with descriptive summaries for qualifying relapse, 6MCDP, or MRI activity and NEDA	A descriptive summary of number and proportion of participants with event A descriptive summary of time to earliest event (overall and by type of event, i.e., qualifying relapse, 6MCDP, or MRI activity).	Missings will be presented in a separate category

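### The primary NEDA-3 uses 6-month instead of the protocol's 3-month confirmed progression, and no visible analysis reports the 3-month version; the effect is probably small and one sensitivity row would show it

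*SAP*

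**What the plan says.** **Protocol.** Section 8.1.2.1 gives the rule: "Sustained EDSS progression is defined as EDSS progression (as defined above) confirmed by subsequent measurements of at least 3 months apart". Section 8.1.4 defines CDP as a sustained EDSS increase, and section 8.1.5 makes that CDP one of the three NEDA-3 components. The protocol's primary endpoint therefore carries the 3-month rule.

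**SAP.** Section 7 lists the departure openly: "6-months confirmed disability progression (6MCDP), is used in the IAP to keep consistent with the parent study IAP", and adds "although 3 months confirmed disability progression, 3MCDP, is defined in the CSP". Section 14.1.1 builds the primary NEDA-3 on 6MCDP. The rise must be present at two assessments in the Extension Study Period "at least 166 days apart (to be consistent with the parent study minimum visit gap"), with no lower score between them. The event is dated at the earlier assessment.

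Section 14.1.2 opens with "The robustness of the results of the primary analysis will be evaluated by the following" and then plans the Treatment Completer Set, the prior-DMD subgroup and a crude summary. All of these keep 6MCDP. So do the visible secondary analyses with a progression component (14.2.1 to 14.2.3). The endpoint table in SAP 5 says only CDP, without an interval.

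**The concern.** The study is single-arm and tests no hypothesis (protocol 9.1), so its product is an estimate, and the definition of the event is part of that estimate. Consistency with the parent study is a reason to report the 6-month version. It is not a reason to leave out the version that the protocol names.

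The two rules are nested, so for any one participant the change can only remove or delay a progression event. A reader of the results cannot tell whether the protocol's own endpoint would have given the same figure or one a few points lower. Because SAP 5 uses the unqualified label CDP, the SAP version could also be mistaken for the protocol version.

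**Working it through.** The plan has no figure to reproduce: the sample-size section is redacted, and no expected NEDA-3 proportion or event rate is given. Throughout, I take the EDSS thresholds and the parent-study Baseline to be the same under both rules, and 3 months as 91 days (3 × 30.4375 = 91.3).

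**1. Scheduled visits.** SAP 9.5 puts Visit 1 (M36) at day 360 ± 30 after M24 and Visit 2 (M48) at day 720 ± 30.
- Shortest interval: 690 − 390 = 300 days.
- Longest interval: 750 − 330 = 420 days.

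Both exceed 166 days, so on scheduled in-window EDSS the two rules give the same result.

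**2. Other EDSS.** The rules can differ only for a pair of raised scores 91 to 165 days apart (about 3 to 5.5 months). Days below are nominal, counted from M24.

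| Route | First raised EDSS | Second raised EDSS | 3-month rule | 6-month rule |
|---|---|---|---|---|
| Early withdrawal after Visit 1 | day 360 | days 451–525 (360 + 91 to 360 + 165) | event, day 360 | no event on actual dates; possibly an event if the withdrawal visit is mapped to M48 |
| Gap period | extension Baseline, days 195–269 (360 − 165 to 360 − 91) | Visit 1, day 360 | event at extension Baseline | same event if the rise persists at Visit 2, which is 451–525 days after that Baseline (720 − 269 to 720 − 195); otherwise none |
| Unscheduled, example | Visit 1, day 360 | day 480 (120 days later) | event, day 360 | same event if the rise persists at Visit 2 (360 days later); otherwise none |

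These routes are open. The Early Withdrawal visit includes EDSS (protocol 1.3). SAP 11.3 counts EDSS from gap participants towards progression. SAP 10.1 has a gap class of 6 to 9 months, and days 195–269 are 6.4 to 8.8 months. In the gap and unscheduled routes a difference also needs the rise to have gone by Visit 2, or no later EDSS to exist.

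**3. Direction for one participant.** Two raised scores at least 166 days apart, with none lower between them, are also at least 3 months apart. Every 6-month event is therefore a 3-month event, and it never starts earlier than the 3-month event.

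**4. Direction for the reported figures.** Turning an event into a later censoring raises the KM estimate or leaves it unchanged. Delaying an event can lower it. Take seven participants: events at days 10 and 70, censorings at days 50, 50, 60, 60 and 720. KM at day 720 is 6/7 × 1/2 = 0.43. If the first event is dated day 65 instead, it is 2/3 × 1/2 = 0.33.

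I simulated 1,500 trials of 60 participants with assumed inputs (15% early withdrawal, 35% with a relapse or MRI event, 40% with a gap-period EDSS, 15% prone to raised scores; 3 months taken as 90 days):
- The nesting in step 3 was never violated.
- KM at day 720, 6-month minus 3-month: unchanged in 1,080, higher in 362, lower in 58; mean +0.4 points, range −1.7 to +5.0.
- Crude NEDA-3 under the 6-month rule: lower in 536, higher in 174.

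The crude figure can fall because SAP 14.1.1 needs two EDSS at least 166 days apart before it records no 6MCDP. A shorter span becomes Unknown but stays in the denominator. This assumes that both EDSS must lie in the Extension Study Period. One participant in 60 is 1.7 points, so only the signs carry over to this study, not the sizes.

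**5. Size.** The protocol plans 200 to 220 evaluable participants.
- One participant: 1/220 = 0.45 points to 1/200 = 0.50 points.
- 95% half-width at p = 0.5: 1.96 × √(0.25/220) = 6.6 points; 1.96 × √(0.25/200) = 6.9 points.
- Six discordant participants: 2.7 points (n = 220) to 3.0 points (n = 200).
- To exceed the half-width: 14 of 200 (7.0 points) or 15 of 220 (6.8 points).

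**The case against.** The case for leaving the SAP as it is has real weight. The change is declared in SAP 7 with a reason. The SAP pools parent and extension data for progression, so one definition across both studies is a sensible choice. The study is exploratory, so neither alpha nor power is touched. Scheduled visits cannot produce a difference. The only mandated unscheduled EDSS is for a suspected relapse, and a qualifying relapse already ends NEDA-3. All of this stands, and it limits the likely size. It does not close every route: a suspected relapse may fail the criteria of protocol 8.1.3.1, unscheduled visits are also at the investigator's discretion, and Early Withdrawal and gap-period EDSS need no relapse.

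The early-withdrawal route is itself open to question. SAP 9.5 maps withdrawal assessments to the nearest planned visit with a missing assessment, which after a completed Visit 1 is M48, and treats delayed assessments as if made at the nominal time. On that reading the two scores are 360 nominal days apart and 6MCDP could be met. SAP 14.1.1 dates the event from the assessment but does not say which dates the 166 days are counted from.

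A reader might infer three stronger things that the documents do not support:
- *That the protocol-defined endpoint is never reported.* Parts of SAP 14 are redacted, so a 3-month analysis there cannot be excluded. Only its absence from the visible analyses can be stated.
- *That the change can only raise NEDA-3.* This is true of a participant's event status, but not strictly of the KM estimate or the crude summary (step 4).
- *That it removes the participants who worsen and then leave.* This depends on the unresolved reading of SAP 9.5.

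**Conclusion.** The concern holds in a limited form. The primary NEDA-3 in the SAP is not the one that the protocol defines, and neither it, its listed sensitivity analyses nor any visible secondary analysis shows the 3-month version. The departure is disclosed and defensible; what is missing is the comparison.

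The expected direction is a higher KM NEDA-3 under the 6-month rule, with occasional exceptions. The number of discordant participants is not given, and any percentage would be a guess. It is probably small, because such a participant needs an EDSS pair about 3 to 5.5 months apart, no later confirmation, and no qualifying relapse or MRI activity. At 0.45 to 0.50 points each, a handful would stay well inside the confidence interval. This is a cheap improvement to the plan, not an error that overturns the primary result. It rests on identical thresholds and Baseline under both rules and on 200 to 220 evaluable participants.

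**What to change.** - Add one row to SAP 14.1.2: 'Sensitivity (FAS): primary derivation with CDP confirmed at least 3 months apart, as in protocol 8.1.2.1', with the same KM method, and give the 3 months as a number of days.
- State in SAP 14.1.1 that the confirmation interval is computed from actual assessment dates, so that the SAP 9.5 mapping does not decide it.
- Report how many participants the two rules classify differently. If there are none, one line settles the matter.
- In the CSR, label the 3-month version as the protocol-defined endpoint and the 6-month version as the SAP modification, and show them together.

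If the SAP can no longer be amended, the same analysis can go into the CSR identified as unplanned, as SAP 4 provides.

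Cost: SAP wording and one extra flag from EDSS data already collected. The second figure may be slightly less favourable, and 3-month confirmation is less specific.

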8.1 Definition of Analysis Sets

Enrolled Set (ES)

All participants who provided informed consent.

Full Analysis Set (FAS)

The FAS will include all enrolled, eligible participants.

Safety Analysis Population (SAF)

All participants treated with at least one dose of cladribine tablets during the parent study.

Treatment Completer Set (TCS)

All participants from the FAS who completed the full treatment course of the first and second year in the parent study (i.e., participants who were in TCS-2 as defined in MAGNIFY MS IAP version 3.0).

Analyses per Analysis Set

Unless otherwise specified, all efficacy analyses will be performed on the FAS and all safety analyses will be performed on the SAF. The primary analysis will also be repeated on the TCS as a sensitivity analysis.

If not stated otherwise, disposition of participants will be summarized on the ES, previous and concomitant medications will be summarized on the FAS, and the analyses on demographics and other baseline characteristics will be based on the FAS.

8.2 Subgroup Definition and Parameterization

Subgroup analyses will be performed on subgroups as defined below.

- Previous (prior to parent study Baseline) treatment with DMDs:
 - o DMD pre-treated: Participants will be categorized as DMD pre-treated if they have taken DMDs any time before start of study medication.
 - o Pre-treatment naïve: all participants not classified as DMD pre-treated.

Details of the definition of DMDs used for subgroups classification are specified in MAGNIFY MS IAP version 3.0. The updated list of DMDs (Appendix 18.1) will be used to identify DMD in concomitant medications in the Extension Study.

All descriptive statistical analyses will be presented separately for the DMD subgroups. The primary analysis, secondary analyses and selected exploratory analyses will also be repeated for this subgroup.

Subset analyses will be performed on the subsets defined as follows:

- Participants with NEDA-3 during Course 1 Treatment Period
- Participants with NEDA-3 during Course 2 Treatment Period

Secondary analyses of NEDA-3 during Year 3 Visit Period and during Year 4 Visit Period (see Section 14.2.1) will be repeated on these subsets. Definition of NEDA-3 during Course 1 Treatment Period and Course 2 Treatment Period is described in Section 14.2.1.

9 General Specifications for Data Analyses

Unless otherwise specified, continuous variables will be summarized using descriptive statistics, i.e., the number of participants with non-missing values (n), mean, standard deviation, median, 25th percentile (Q1) and 75th percentile (Q3), minimum, and maximum.

Qualitative variables will be summarized by frequency counts and percentages. Unless otherwise stated the calculation of proportions will be based on the number of participants of the analysis set of interest. Therefore, counts of missing observations will be included in the denominator and presented as a separate category.

Descriptive statistics by nominal visit or time point will include only data from scheduled visits. Unscheduled visits will be included in the derivation of baseline or worst on-treatment values.

All statistical tests mentioned in this IAP are to be regarded as descriptive and exploratory, and differences with a p-value of 0.05 or less will be considered nominally statistically significant. No correction for multiple testing will be applied for any of the analyses. If confidence intervals (CI) are to be calculated, these will be two-sided with a confidence probability of 95%, unless otherwise specified in this IAP.

Study data will be integrated with study data from the MAGNIFY MS trial as required to perform the statistical analyses, i.e., study data up to M24 visit is integrated from the MAGNIFY MS trial.

If not specified otherwise, all listings will only include data collected in the Extension Study, including the gap period between the MAGNIFY MS trial and MAGNIFY MS Extension Study. Listings regarding demographic and other Baseline characteristics will include data from MAGNIFY MS Baseline.

If data from parent study are used, all rules from parent study IAP still apply for the analysis of these data, except alternative rules are explicitly specified in this IAP.

All analyses will be performed using SAS® Software version 9.4 or higher or R (http://www.r-project.org/), Version 3.6.3 or higher as applicable.

